8.4.5 Pregnancy and Exposure During Breastfeeding

Although pregnancy and infant exposure during breastfeeding are not considered AEs, any pregnancy or infant exposure during breastfeeding in a participant (spontaneously reported to the investigator or their designee) that occurs during the study are reportable to MSD.

All reported pregnancies must be followed to the completion/termination of the pregnancy.

Any pregnancy complication will be reported as an AE or SAE.

The medical reason (example: maternal health or fetal disease) for an elective termination of a pregnancy will be reported as an AE or SAE. Prenatal testing showing fetus will be born with severe abnormalities/congenital anomalies that leads to an elective termination of a pregnancy will be reported as an SAE for the fetus.

Pregnancy outcomes of ectopic pregnancy, spontaneous abortion, missed abortion, benign hydatidiform mole, blighted ovum, fetal death, intrauterine death, miscarriage, and stillbirth must be reported as serious events (Important Medical Events). If the pregnancy continues to term, the outcome (health of infant) must also be reported.

8.4.6 Disease-related Events and/or Disease-related Outcomes Not Qualifying as AEs or SAEs

Not applicable for this study.

8.4.7 Adverse Events Reported on the eVRC

Participants will use an eVRC to report solicited and unsolicited AEs (Section 8.1.11).

The definitions of solicited and unsolicited AEs are provided in Appendix 3.

8.4.7.1 Solicited Adverse Events

Solicited AEs for this study are summarized in [Table 4](#).

Table 4 Solicited Adverse Events for V181-002

Type of Solicited Adverse Event	Predefined Solicited Adverse Events	Solicited Time Period
Injection site	
• Injection-site pain/tenderness• Injection-site erythema/redness• Injection-site swelling	Day 1 through Day 5 postvaccination
Systemic	
• Rash• Headache• Fatigue (tiredness)• Myalgia (muscle pain)• Arthralgia (joint pain)	Day 1 through Day 28 postvaccination

All solicited injection-site AEs will be considered related to study intervention. The investigator will assess all solicited injection-site AEs for overall intensity grade, and all systemic AEs for both overall intensity grade and causality (Appendix 3).

In addition, the investigator will review all solicited AEs for the following:

- Is the event a symptom of another diagnosis?
- Is the event ongoing at the end of the solicited period?
- Does the event meet serious criteria?

Investigators are responsible for reviewing, assessing, and reporting data entered in the eVRC on the appropriate eCRF(s) as specified in the data entry guidelines. In addition, solicited injection-site AEs and solicited systemic AEs reported by the participant using the eVRC will be transferred directly to MSD's database.

8.4.7.2 Unsolicited Adverse Events

Unsolicited AEs for this study are events that are 1) not predefined in [Table 4](#), or 2) predefined in [Table 4](#), but reported at any time outside the solicited time period. Unsolicited AEs reported by the participant will be entered by study-site personnel on the appropriate eCRF.

As described in Section 8.4, the investigator will assess unsolicited events that meet the definition of an AE or SAE with respect to seriousness, overall intensity grade, and causality.

8.4.8 Events of Clinical Interest

No specific ECIs will be collected for this study.

8.5 Treatment of Overdose

In this study, an overdose is any dose higher than 1 dose of the investigational V181 or Butantan-DV.

No specific information is available on the treatment of overdose.

8.6 Pharmacokinetics

PK parameters will not be evaluated in this study.

8.7 Pharmacodynamics

Pharmacodynamic parameters will not be evaluated in this study.

8.8 Visit Requirements

Visit requirements are outlined in Section 1.3. Specific procedure-related details are provided in Section 8.

8.8.1 Screening

Prior to randomization, potential participants will be evaluated to determine that they fulfill the entry requirements as set forth in Section 5. Screening procedures will be conducted at Visit 1 (Day 1) and may be repeated after consultation with MSD.

8.8.2 Treatment Period/Vaccination Visit

Requirements during the treatment period are outlined in Section 1.3.

9 STATISTICAL ANALYSIS PLAN

This section outlines the statistical analysis strategy and procedures for the study. If, after the study has begun, but prior to any unblinding, changes are made to primary and/or key secondary hypotheses, or the statistical methods related to those hypotheses, then the protocol will be amended (consistent with ICH Guideline E-9). Changes to exploratory or the nonconfirmatory analyses made after the protocol has been finalized, but prior to unblinding, will be documented in an sSAP and referenced in the CSR for the study. Post hoc exploratory analyses will be clearly identified in the CSR.

9.1 Statistical Analysis Plan Summary

Key elements of the SAP are summarized below; the comprehensive plan is provided in Sections 9.2 to 9.12.

Study Design Overview	A Phase 2, Randomized, Double-Blind, Multicenter, Safety and Immunogenicity Clinical Bridging Study to Compare V181 (Dengue Quadrivalent Vaccine rDENVΔ30 [live, attenuated]) to Butantan Dengue Vaccine (Butantan-DV) in Healthy Adults 18 to 50 Years of Age in Brazil
Treatment Assignment	There are 2 vaccination arms. Participants will be assigned randomly in a 1:1 ratio to receive V181 or Butantan-DV using an IRT. A double-blind/masking technique will be used.
Analysis Populations	Immunogenicity: PP Population Safety: APaT
Primary Endpoint(s)	Immunogenicity (Primary): DENV-neutralizing antibody GMTs for each of the 4 dengue serotypes at Day 28 postvaccination as measured by VRNT DENV-neutralizing antibody seroconversion rates for each of the 4 dengue serotypes at Day 28 postvaccination as measured by the VRNT. Seroconversion is defined as achieving a serotype-specific VRNT titer \geq LLOQ at Day 28 postvaccination in participants who are seronegative at baseline. Safety (Primary): Vaccine-related SAEs from Day 1 through Day 28 postvaccination

Key Secondary Endpoints	
Safety (Secondary):
 
Solicited injection-site AEs of pain, erythema, and swelling from Day 1 through Day 5 postvaccination
 
Solicited systemic AEs of rash, headache, fatigue (tiredness), myalgia (muscle pain) and arthralgia (joint pain), from Day 1 through Day 28 postvaccination

Statistical Methods for Key Immunogenicity Analyses	
To address the primary immunogenicity non-inferiority objective in terms of GMTs (H1), the comparison between groups will be made based on serotype-specific antibody GMTs for the 4 dengue serotypes at Day 28 postvaccination. The estimation of the GMT ratios and the corresponding 95% CIs will be calculated using a linear model with the log-transformed antibody titer as the response and a single term for vaccination group.
 
To address the primary immunogenicity non-inferiority objective in terms of seroconversion rates (H2), the comparison between groups will be made based on serotype-specific antibody seroconversion rates for the 4 dengue serotypes at Day 28 postvaccination. The between-treatment difference (V181 minus Butantan-DV) and its 95% CI will be calculated using M&N method [Miettinen, O. and Nurminen, M. 1985].

Statistical Methods for Key Safety Analyses	For overall safety endpoints and specific AEs point estimates and 95% CIs for the differences between treatment groups in the percentages of participants with events will be provided using the M&N method [Miettinen, O. and Nurminen, M. 1985].
Interim Analyses	There are no planned interim analyses for this study.
Multiplicity	The study will be considered to have met its primary objectives for immunogenicity if, at Day 28 postvaccination, V181 is demonstrated non-inferior to Butantan-DV for the 4 dengue serotypes for both primary endpoints (virus-neutralizing antibody GMTs and virus-neutralizing antibody seroconversion rates). All hypotheses will be tested individually for each serotype at a 1-sided 0.025 alpha level. This approach controls the 1 sided type-I error rate at 0.025, thus no multiplicity adjustment is required.
Sample Size and Power	
Immunogenicity: This study will randomize participants in a 1:1 ratio into the 2 vaccination groups (V181 vs Butantan-DV). The overall sample size will be approximately 1240 with 620 participants in each vaccination group. This sample size ensures sufficient power (approximately 90%) to assess the endpoints for both primary hypotheses. All statistical tests will be conducted at a 1-sided 2.5% alpha level. Details are provided in Section 9.9.1
 
Safety: If no vaccine-related SAEs are observed among the 620 participants in each vaccination group, this study will provide 97.5% confidence that the underlying percentage of participants with vaccine-related SAEs is <0.6% in each vaccination group.

9.2 Responsibility for Analyses/In-house Blinding

The statistical analysis of the data obtained from this study will be the responsibility of the Clinical Biostatistics department of MSD. This study will be conducted as a double-blind study under in-house blinding procedures.

The Clinical Biostatistics department will generate the randomized allocation schedule(s) for study vaccination assignment. Randomization will be implemented in an IRT.

The primary safety and immunogenicity evaluation period for this study is defined as the period from Day 1 through Day 28 postvaccination. A CSR will be produced to present the results for this time period. The official, final database for the Day 28 analysis will not be unblinded until medical/scientific review has been performed, protocol deviations have been identified, and data have been declared final and complete. After the Day 28 postvaccination visit, participants will be followed for safety (MAAEs, SAEs, deaths, and dengue-related events only) and immunogenicity through Month 12 postvaccination. Results for the Month 3 immunogenicity endpoints may be analyzed separately after Month 3 VRNT results become available and protocol deviations have been identified. Results for the remainder of the study through Month 12 postvaccination time period will be presented in a final, separate study report.

After the database lock for the primary analysis, most Sponsor and MSD Headquarters personnel involved in the conduct of the trial will be unblinded to vaccination group assignments. A blinded MSD Headquarters medical monitoring team will monitor the study after Day 28 through Month 12 postvaccination. Participants, investigators, study-site personnel, and MSD field personnel or delegates (eg, blinded Clinical Research Associate) will remain blinded to vaccination group assignments until the final study analyses are completed following the Month 12 (final) database lock.

9.3 Hypotheses/Estimation

Objectives and hypotheses of the study are stated in Section 3.

9.4 Analysis Endpoints

Immunogenicity and safety endpoints that will be evaluated are listed below.

9.4.1 Immunogenicity and Viremia Endpoints

Primary Immunogenicity Endpoints

- DENV-neutralizing antibody GMTs for each of the 4 dengue serotypes at Day 28 postvaccination as measured by VRNT.
- DENV-neutralizing antibody seroconversion rates for each of the 4 dengue serotypes at Day 28 postvaccination as measured by VRNT. Seroconversion is defined as achieving a serotype-specific VRNT titer \geq LLOQ at Day 28 postvaccination in participants who are seronegative at baseline. For participants who are seropositive at baseline (included in the FAS population) seroconversion is defined as achieving a 4-fold rise in serotype-specific VRNT titer at Day 28 postvaccination. Further information on the LLOQ will be documented in the sSAP.

Additional Immunogenicity and Viremia Endpoints

CCI

9.4.2 Safety Endpoints

An initial description of safety measures is provided in Section 4.2.1.2. The overall safety and tolerability profile for each vaccine will be assessed by clinical review of all safety data collected. Solicited and unsolicited injection-site and systemic AEs will be summarized overall, and by maximum reported intensity. The primary safety evaluation period for this study will be Day 1 through Day 28 postvaccination.

Primary Safety Endpoints

- Vaccine-related SAEs from Day 1 through Day 28 postvaccination

Secondary Safety Endpoints

- Solicited injection-site AEs of injection-site pain, injection-site erythema, and injection-site swelling from Day 1 through Day 5 postvaccination
- Solicited systemic AEs of rash, headache, fatigue (tiredness), myalgia (muscle pain), and arthralgia (joint pain) from Day 1 through Day 28 postvaccination

Additional Safety Endpoints

- Unsolicited AEs from Day 1 through Day 28 postvaccination
- Elevated temperature ($\geq 37.8^{\circ}\text{C}$ axillary) from Day 1 through Day 28 postvaccination
- MAAEs, SAEs, deaths, and dengue-related events from Day 1 through Month 12 postvaccination

9.5 Analysis Populations

9.5.1 Immunogenicity Analysis Populations

The PP population will serve as the primary population for the analysis of the immunogenicity data in this study. The PP population excludes participants due to deviations from the protocol that may substantially affect the results of the primary immunogenicity endpoint. Potential deviations that may result in the exclusion of a participant from the PP population for all immunogenicity analyses include:

- Prevaccination baseline blood sample test result is seropositive for any of the 4 dengue serotypes by VRNT. Seropositivity is defined as having a serotype-specific VRNT titer at or above the LLOQ of the assay.
- Failure to receive correct clinical material as per randomization schedule.
- Receipt of prohibited medication or prohibited vaccine prior to study vaccination or through Day 28 postvaccination.
- Collection of a blood sample at the time point for the analysis outside the prespecified window (as described in Section 1.3.1).
- Any virologically confirmed dengue case that occurs prior to the immunogenicity time point (Day 28, Month 3, Month 12 postvaccination) being evaluated.

The final determination on protocol violations, and thereby the composition of the PP population, will be made prior to the unblinding of the database and will be documented in a separate memo. The key immunogenicity analyses will also be performed using the FAS population, which consists of all randomized participants who receive study vaccination and have at least 1 valid serology result. Participants will be included in the vaccination group to which they are randomized for the analysis of immunogenicity data using the FAS population. No adjustment will be made for missing data.

If more than 10% of the participants have seropositive results at baseline, immunogenicity summaries of seropositive participants will also be generated.

9.5.2 Safety Analysis Populations

The APaT population will be used for the analysis of safety data in this study. The APaT population consists of all randomized participants who received at least 1 dose of study vaccine. Participants will be included in the vaccination group corresponding to the study vaccine they actually received for the analysis of safety data using the APaT population. For most participants this will be the vaccination group to which they are randomized.

9.6 Statistical Methods

This section describes the statistical methods that address the primary and secondary objectives. Statistical methods related to exploratory objectives will be further described in

the sSAP. The key immunogenicity analyses to be performed are summarized in [Table 5](#) (Section 9.6.1). The safety analyses are summarized in Section 9.6.2. Unless otherwise stated, all statistical tests will be conducted at the $\alpha=0.05$ (2-sided) level.

9.6.1 Statistical Methods for Immunogenicity Analyses

Primary Endpoints/Hypothesis (H1)

The primary hypothesis of non-inferiority of antibody GMTs for each dengue serotype (DENV1, DENV2, DENV3, and DENV4) will be addressed by 4 one-sided tests of non-inferiority (1 corresponding to each dengue serotype) conducted at $\alpha=0.025$ level (1-sided). For each dengue serotype, the hypotheses to be tested are:

$$H_0: \text{GMT}_1/\text{GMT}_2 \leq 0.67$$

Versus

$$H_1: \text{GMT}_1/\text{GMT}_2 > 0.67$$

where GMT_1 represents the GMT at Day 28 postvaccination in the V181 group and GMT_2 represents the GMT at Day 28 postvaccination in the Butantan-DV group. Estimation of the GMT ratios and computation of the corresponding 95% CIs will be calculated using t-distribution with the variance estimate from a linear model utilizing the log-transformed antibody titer as the response and a single term for vaccination group. The point estimates will be calculated by exponentiating the estimates of the mean of the natural log values and the CIs will be derived by exponentiating the CIs of the mean of the natural log values based on the model. The statistical criterion for non-inferiority requires that the lower bound of 2-sided 95% CI of GMT ratio (V181 vs Butantan-DV) being greater than 0.67.

Primary Endpoints/Hypothesis (H2)

The primary hypothesis of non-inferiority of seroconversion rates for each dengue serotype (DENV1, DENV2, DENV3, and DENV4) will be addressed by 4 one-sided tests of non-inferiority (1 corresponding to each dengue serotype) conducted at $\alpha=0.025$ level (1-sided). For each dengue serotype, the hypotheses to be tested are:

$$H_0: p_1 - p_2 \leq -0.1$$

Versus

$$H_1: p_1 - p_2 > -0.1$$

where p_1 represents the seroconversion rate at Day 28 postvaccination in the V181 group and p_2 represents the seroconversion rate at Day 28 postvaccination in the Butantan-DV group. For each dengue serotypes, V181 is non-inferior to Butantan-DV if the lower bound of the 2-sided 95% CI for the between-treatment differences (V181 minus Butantan-DV) is greater than -0.1. The M&N method an unconditional, asymptotic method, will be used for this analysis [Miettinen, O. and Nurminen, M. 1985].

[figure not shown]

Table 5 Analysis Strategy for Primary Immunogenicity Variables

Endpoint/Variable (Description, Time Point)	Primary vs. Supportive Approach ^a	Statistical Method	Analysis Population	Missing Data Approach
DENV-neutralizing antibody GMTs (H1) for each of the 4 dengue serotypes at Day 28 postvaccination as measured by VRNT	P S	t-distribution with the variance estimate from a linear model ^b (estimate, 95% CI, p-value)	PP FAS	Missing data will not be imputed
DENV-neutralizing antibody seroconversion rates (H2) for each of the 4 dengue serotypes at Day 28 postvaccination as measured by VRNT	P S	Miettinen and Nurminen (estimate, 95% CI, p-value)	PP FAS	Missing data will not be imputed

CI=confidence interval; DENV=dengue virus; FAS=Full Analysis Set; GMT=geometric mean titer; PP=Per-Protocol; VRNT=virus reduction neutralization test

^a P=Primary approach; S=Supportive approach.

^b Estimation of the DENV-neutralizing antibody GMTs and computation of the corresponding 95% CIs will be calculated using t-distribution with the variance estimate from a linear model utilizing the log-transformed antibody titer as the response and a single term for vaccination group.

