9.8 Multiplicity

The study will be considered to have met its primary objectives for immunogenicity if, at Day 28 postvaccination, V181 is demonstrated non-inferior to Butantan-DV for the 4 dengue serotypes for both primary endpoints (DENV-neutralizing antibody GMTs and DENV-neutralizing antibody seroconversion rates). All hypotheses will be tested individually for each serotype at a 1 sided 0.025 alpha level. This approach controls the 1-sided type-I error rate at 0.025, thus no multiplicity adjustment is required.

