9.9 Sample Size and Power Calculations

9.9.1 Sample Size and Power for Immunogenicity Analyses

This study will randomize participants in a 1:1 ratio into the 2 vaccination groups (V181 vs Butantan-DV). The overall sample size will be approximately 1240 with 620 participants in each vaccination group. This sample size ensures sufficient power (approximately 90%) to assess the endpoints for both primary hypotheses. The power for each individual hypothesis is provided below.

Primary Endpoints/Hypothesis (H1)

With this study sample size and the assumptions listed below, the power for the primary hypothesis to establish that V181 is non-inferior to Butantan-DV for all 4 dengue serotypes at an overall 1-sided, 2.5% alpha level based on GMTs is >95%. The power and sample size are based on the following assumptions: 1) an approximately 20% non-evaluable rate (496 evaluable participants per vaccination group) which includes an assumption of 10% of the participants being excluded due to be seropositivity at baseline; 2) the non-inferiority margin of 0.67; 3) the true GMT ratio is assumed to be 1; and [REDACTED]

[REDACTED]

[REDACTED]

Primary Endpoints/Hypothesis (H2)

With the assumptions listed below, the power for the primary hypothesis to establish that V181 is non-inferior to Butantan-DV for all 4 dengue serotypes at an overall 1-sided, 2.5% alpha level based on seroconversion rates is ~90%. The power is based on the following assumptions: 1) an approximately 20% non-evaluable rate (496 evaluable participants per vaccination group) which includes an assumption of 10% of the participants being excluded due to be seropositivity at baseline; 2) the non-inferiority margin of -0.1 for the difference (V181 – Butantan-DV); and [REDACTED]

[REDACTED]

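### The supportive FAS analyses pool baseline-seropositive and seronegative participants without using the scheduled baseline titer, which costs precision and makes a PP/FAS difference harder to read

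*Combined protocol and SAP*

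**What the plan says.** Section 9.5.1 makes PP the primary immunogenicity population and lists a positive baseline VRNT for any serotype among the reasons for exclusion. It then adds: "The key immunogenicity analyses will also be performed using the FAS population". The FAS takes every vaccinated, randomized participant with at least one valid serology result, so baseline serostatus does not remove anyone from it. Section 9.4.1 confirms this and gives such participants their own endpoint rule: "For participants who are seropositive at baseline (included in the FAS population) seroconversion is defined as achieving a 4-fold rise in serotype-specific VRNT titer". Baseline seronegatives need only reach the LLOQ.

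Table 5 lists one method per endpoint and applies it to both PP and FAS. For H1 it is "a linear model utilizing the log-transformed antibody titer as the response and a single term for vaccination group". For H2 it is M&N, with no strata named. A stratified M&N method is named only for safety (Section 9.6.2.1).

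Three other places bear on this:
- Section 2.1 says that exposure to one serotype affects the response to the others and could confound the immunogenicity hypotheses.
- Section 6.3.2 says randomization is not stratified.
- Section 1.3.1 schedules a Day 1 VRNT sample for all participants.

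Section 9.5.1 also promises separate summaries of seropositive participants, but only if they exceed 10% of participants. Section 9.9.1 plans on "an assumption of 10% of the participants being excluded due to be seropositivity at baseline".

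**The concern.** A group-only model is adequate in PP because every known baseline titer there should be below the LLOQ. In the FAS that condition fails by design. If prior immunity predicts the Day 28 titer, the spread between seropositives and seronegatives goes into the residual variance. Any chance difference between arms in the share of seropositives then moves the unadjusted estimate in that particular trial. For H2, two differently defined responses are pooled into one rate per arm.

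What is at stake is how useful the FAS is as a supportive analysis. If PP and FAS disagree, the reader will want to know whether the PP exclusions matter. An unadjusted FAS leaves chance serostatus imbalance as a competing explanation, although the data to remove it are scheduled to be collected.

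**Working it through.** **Inputs from the documents.** 620 per arm, with 20% non-evaluable including 10% for seropositivity (Section 9.9.1). "All hypotheses will be tested individually for each serotype at a 1 sided 0.025 alpha level" (Section 9.8). H1 needs the "lower bound of 2-sided 95% CI of GMT ratio (V181 vs Butantan-DV) being greater than 0.67" (Section 9.6.1). H2 uses "the non-inferiority margin of -0.1 for the difference" (Section 9.9.1).

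**The plan's own figures.** 620 × 0.80 = 496, as stated. The stated powers (above 95% for H1, about 90% for H2) cannot be reproduced because the SD and seroconversion rates are redacted. Neither is implausible. At 496 per arm and a true ratio of 1, H1 power above 95% for all four serotypes allows an ln SD of up to about 1.50 if serotypes are independent, or 1.75 if fully correlated. H2 power of 90% with four independent serotypes needs a common rate near 0.795.

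**Assumptions, not in the documents.** FAS of 558 per arm (620 × 0.90, i.e. the other 10% non-evaluable also missing from the FAS); share seropositive π = 0.10; Day 28 titers f = 3 to 10 times higher in seropositives; within-stratum SD of ln titer 1.0 to 1.5. The calculations cover a serostatus term only.

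**Step 1: precision, H1.** Variance inflation from omitting serostatus = 1 + π(1 − π)(ln f)² / SD².
- f = 3, SD 1.5: 1 + 0.09 × 1.207 / 2.25 = 1.048.
- f = 10, SD 1.0: 1 + 0.09 × 5.302 / 1.0 = 1.477.

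The reduction in CI width on the log scale is 1 − 1/√inflation: 2.3% and 17.7%.

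**Step 2: FAS against PP.** Take SD 1.5 and f = 10.
- Unadjusted FAS: SE = √[2(2.25 + 0.477)/558] = 0.0989.
- Adjusted FAS: SE = √[2 × 2.25/558] = 0.0898.
- PP: SE = √[2 × 2.25/496] = 0.0952.

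Here the unadjusted FAS is less precise than PP despite having more participants. Per-serotype power is 98.2% unadjusted against 99.4% adjusted, so the power cost is small.

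**Step 3: chance imbalance, H1.** A 2-SE difference between arms in the share seropositive is 2√(2 × 0.1 × 0.9/558) = 0.036, or 3.6 points. The ratio moves by exp(0.036 × ln f): 1.04 for f = 3 and 1.086 for f = 10.

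**Step 4: is there bias?** In 5,000 simulated trials (SD 1.5, f = 10, π = 0.10), mean bias was about 0.001 on the ln scale both without and with a serostatus term. CI coverage was 95.8% and 95.6%. The empirical SD of the estimate was 0.097 and 0.088. So there is no bias over randomization, only lost precision.

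**Step 5: H2.** With assumed seronegative rates of 0.75 to 0.90 and seropositive 4-fold-rise rates of 0.1 to 0.9, the ratio of unadjusted to stratified SE runs from 1.00 (similar rates) to 1.28. The 95% chance shift is at most 2.8 points, against a 10-point margin. The largest power loss is about 2.8 points (94.9% against 97.7%).

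**Step 6: what adjustment does not do.** Suppose the vaccines do not differ in seropositives and the true seronegative ratio sits at the margin. The pooled FAS ratio is then 0.67^0.9 = 0.697, and a −10-point difference becomes −9. In simulation at that H1 boundary (SD 1.5, f = 10), the FAS passed in 5.6% of trials unadjusted and 6.6% adjusted, against a nominal 2.5%. Pooling dilutes a seronegative deficit with or without the covariate.

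**The case against.** The strongest reply is that this is an efficiency preference about an analysis that decides nothing. Table 5 labels the FAS supportive, and H1 and H2 rest on PP, where seropositives are to be excluded. "This study will randomize participants in a 1:1 ratio into the 2 vaccination groups", so the group-only estimate is unbiased and its interval already allows for chance imbalance. Extra noise makes the FAS harder to pass, so it cannot manufacture support for PP. All of that stands.

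The sizes are also assumed. The upper figures need a 10-fold difference together with an SD of 1.0. Seropositives who reach the FAS should have had a negative point-of-care antibody test and no known dengue or Zika history, so strong prior immunity cannot be presumed. The 4-fold-rise rule already conditions on each participant's own baseline. These points stand too, and they limit the size of the finding.

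Three objections to the remedy carry less weight.
- **One model for both sets.** Using the same model isolates the effect of population. But serostatus is constant where all participants are seronegative, so a model with the covariate reduces to the PP model there.
- **Missing baselines.** The FAS requires only one valid serology result, so a covariate could drop people. A missing-baseline category keeps them in H1.
- **Dilution is not cured.** True, but dilution belongs to the pooled quantity itself and is answered by reporting results by serostatus.

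**Conclusion.** The point holds as a modest, inexpensive improvement to the supportive analyses. The FAS comparison ignores a baseline measurement that the plan schedules for everyone and treats as relevant to response. Under the stated assumptions the gain is a GMT-ratio interval about 2% to 18% narrower, and protection against a shift of about 4% to 9% from a 2-SE imbalance. That shift compares with a margin that allows a 33% reduction. For H2 the gain ranges from nothing to a moderate gain in precision, depending on how far response rates differ between strata.

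A reader might infer more, and the documents do not support it:
- **That the FAS result is biased.** Randomization and the simulation rule this out; only the realized shift in a single trial remains.
- **That the non-inferiority conclusion is at risk.** It is drawn from PP, where seropositives are to be excluded.
- **That the FAS is the only check on PP.** Section 9.10 on subgroups is redacted and the supplemental SAP is not available, so this cannot be asserted.

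The conditional seropositive summaries do not close the gap. At exactly the planned 10% they are not triggered, and they are not an adjusted comparison.

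**What to change.** For the FAS rows of Table 5:
- **H1:** add baseline serostatus (seropositive to any serotype, matching the PP exclusion) and the serotype-specific log baseline titer, with results below the LLOQ set to a fixed value. Keep participants without a valid baseline through a missing-baseline category.
- **H2:** use M&N stratified by the same serostatus.
- **Both:** report FAS results by serostatus whatever the percentage seropositive, because adjustment does not remove dilution of a seronegative deficit.

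Leave the PP analysis unchanged. If Day 28 data are still blinded, document the change by the route in Section 9. If they have been unblinded, present it as a labelled post hoc sensitivity analysis. The cost is slightly more analysis work and one extra rule for missing baselines; no new data collection is needed.
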